1 SYNOPSIS

Title: A Phase 3b/4 Randomized, Open-label, Efficacy Assessor Blinded Study, Comparing the Safety and Assessor Blinded Efficacy of Upadacitinib to Dupilumab in Subjects with Moderate to Severe Atopic Dermatitis (Level-Up)	
Background and Rationale:	
Upadacitinib is an oral, once-daily, selective, and reversible small-molecule JAK inhibitor, engineered to have greater inhibitory potency for JAK1 versus JAK2, JAK3, and tyrosine kinase 2 (TYK2). Janus kinase 1 inhibition blocks the signaling of many important pro-inflammatory cytokines, including interleukin (IL)-2, IL-6, IL-7, and IL-15, interferon (IFN)-γ, which are known contributors to inflammatory disorders. It also blocks the signaling of IL-4, IL-13, IL-31, IL-22, IFN-γ, thymic stromal lymphopoietin (TSLP) cytokines that play an important role in the pathogenesis of atopic dermatitis (AD).
 
Upadacitinib has been approved in at least one country for the treatment of moderate to severe/active immune mediated inflammatory diseases such as rheumatoid arthritis, psoriatic arthritis, ankylosing spondylitis, non-radiographic axial spondyloarthritis, ulcerative colitis, Crohn's disease, and AD.
 
Dupilumab is a recombinant human IgG4 monoclonal antibody that inhibits interleukin-4 and interleukin-13 signaling. Dupilumab inhibits IL-4 signaling via the Type I receptor (IL-4Rα/γc), and both IL-4 and IL-13 signaling through the Type II receptor (IL-4Rα/IL-13Rα).
 
Dupilumab has been approved in at least one country for the treatment of moderate to severe AD, moderate to severe asthma, chronic rhinosinusitis with nasal polyposis, eosinophilic esophagitis, and prurigo nodularis.
 
This study aims to provide data on the efficacy and safety of upadacitinib initiated at 15 mg QD and dose escalated based on the clinical response, compared with dupilumab as per its label, after 16 weeks of treatment.

Objective(s) and Endpoint(s):	
Primary Objective
 
The primary study objective, related to Study Period 1, is to assess the efficacy and safety of upadacitinib, initiated at 15 mg once daily (QD) and dose adjusted based on clinical response, compared with dupilumab as per its label.
 
An additional objective, related to Study Period 2, is to assess the efficacy and safety of upadacitinib, initiated at 15 mg QD, and dose adjusted based on clinical response, in subjects with inadequate response to dupilumab.
 
The primary efficacy objective is based on the achievement of a composite endpoint of at least a 90% reduction in Eczema Area and Severity Index from baseline (EASI 90) and a Worst Pruritus Numerical Rating Scale of 0 or 1 (WP-NRS 0/1) at Week 16 with the treatment of upadacitinib compared with dupilumab in the Intent-to-Treat (ITT) Population.
 
Primary Endpoint
 
The primary endpoint is the achievement of a composite endpoint of both EASI 90 and WP-NRS 0/1 at Week 16.

	
Ranked Secondary Endpoints
 
The ranked secondary endpoints are:
 
 1. Achievement of EASI 90 at Week 16. 2. Achievement of WP-NRS 0/1 at Week 16 among subjects with Baseline WP-NRS > 1. 3. Achievement of an improvement (reduction) in WP-NRS \geq 4 at Week 16 among subjects with Baseline WP-NRS \geq 4. 4. Achievement of WP-NRS 0/1 at Week 4 among subjects with Baseline WP-NRS > 1. 5. Achievement of WP-NRS 0/1 at Week 2 among subjects with Baseline WP-NRS > 1. 6. Achievement of EASI 90 at Week 4. 7. Achievement of EASI 75 at Week 2. 8. Achievement of EASI 100 at Week 16. 
Safety Endpoints
 
Safety will be assessed by AE monitoring, physical examination, vital signs, and clinical laboratory testing during the study. Laboratory assessments will include hematologic parameters, chemistry, liver function tests, and lipid parameters.

Investigator(s):	Multicenter.
Study Site(s):	Up to 330 sites globally
Study Population and Number of Subjects to be Enrolled:	Approximately 880 adolescent and adult subjects (\geq 12 and < 64 years of age and weighing at least 40 kg) with moderate to severe AD who have inadequate response to systemic therapies.
Investigational Plan:	
This is a Phase 3b/4, global, randomized, open-label, efficacy assessor blinded, multi-center study that will evaluate upadacitinib compared with dupilumab, as monotherapy, in adolescents and adult subjects (\geq 12 and < 64 years of age, weighing at least 40 kg) with moderate to severe AD who have inadequate response to systemic therapy. Eligible subjects must have a documented history of inadequate response to at least one systemic treatment for AD prior to the Baseline Visit or for whom other systemic treatments are otherwise medically inadvisable.
 
The study will consist of a 35-day Screening Period; Period 1, a 16-week randomized, open-label, efficacy assessor blinded treatment period for all subjects, and a 30-day or 12-week (84 days) follow-up visit for subjects on upadacitinib or dupilumab respectively, who will not enter Period 2; Period 2, a 16-week open-label, efficacy assessor blinded extension period for those subjects with a < EASI 75 response at Week 16 (total duration 32 weeks) and a 30-day follow-up visit.
 
After the last study visit, a 30-day or 12-week (for subjects receiving upadacitinib or dupilumab, respectively) follow-up visit (or phone call if a visit is not possible) will be completed to determine the status of any new or ongoing AEs/SAEs and concomitant medications.
 
The 30-day or 12-week follow-up phone call (for subjects on upadacitinib or dupilumab, respectively) following the last dose of study drug will not be

	
required for any subject who initiates commercially available upadacitinib or dupilumab upon the study Completion Visit or Premature Discontinuation visit.
 
The study is comprised of two periods:
 
 Period 1: A 16-week open-label, efficacy assessor blinded treatment period to evaluate the efficacy and safety of upadacitinib, initiated at 15 mg QD and dose adjusted based on clinical response starting after 4 weeks of treatment, compared with dupilumab as per its label. 
Subjects who meet eligibility criteria will be randomized in a 1:1 ratio to receive either upadacitinib 15 mg QD or dupilumab as per its label. During Period 1, subjects randomized to upadacitinib 15 mg QD will have their dose increased to 30 mg QD if any of the following parameters is met:
 
 Starting at Week 4, subject has a < EASI 50 response. Starting at Week 4, subject has a < 4-point improvement from Baseline in WP-NRS (weekly average). Starting at Week 8, subject has a < EASI 75 response. 
 Period 2: An extension period to evaluate the efficacy and safety of upadacitinib, initiated at 15 mg QD and dose adjusted based on clinical response, in subjects with inadequate response to dupilumab, and treatment at 30 mg QD in subjects with inadequate response to upadacitinib in Period 1. 
At Week 16 subjects from both treatment arms in Period 1 with a < EASI 75 response will enter Period 2; subjects from the dupilumab arm will be offered the option to receive upadacitinib 15 mg QD while subjects from the upadacitinib arm will either continue (if already receiving 30 mg QD) or be escalated to upadacitinib 30 mg QD (if receiving 15 mg QD) until Week 32.
 
 During Period 2, subjects receiving upadacitinib 15 mg QD will have their dose increased to 30 mg QD if any of the following parameters is met: 
 Starting at Week 20, subject has a < EASI 75 response. Starting at Week 20, subject has a < 4-point improvement from Baseline in WP-NRS (weekly average) 
Rescue Therapy
 
Period 1
 
Upadacitinib arm: Starting four weeks following dose escalation to upadacitinib 30 mg QD in Period 1, subjects with a < EASI 50 response or < 4-point improvement from Baseline in WP-NRS (weekly average) will have the option to add topical therapy (except for topical JAK inhibitors) as rescue therapy.
 
Dupilumab arm: Starting at Week 4 of Period 1 with dupilumab as per its label, subjects with a < EASI 50 response or < 4 point improvement from Baseline in WP-NRS (weekly average), will have the option to add topical therapy (except for topical JAK inhibitors) as rescue therapy.

--	--

	
Period 2
 
Starting four weeks following dose escalation to upadacitinib 30 mg QD in Period 2, subjects with a < EASI 75 response from Baseline or < 4-point improvement from Baseline in WP-NRS (weekly average) will have the option to add topical therapy (except for topical JAK inhibitors) as rescue therapy.

Key Eligibility Criteria:	
Key eligibility criteria include:
 
 1. Subjects ≥ 12 years old (≥ 40 kg at Baseline) and < 64 years old at Screening Visit. Subject must not turn 65 years old before completing the study. 2. Chronic AD with onset of symptoms at least 3 years prior to baseline and subject meets Hanifin and Rajka criteria. 3. EASI score ≥ 16; vIGA-AD score ≥ 3 and $\geq 10\%$ BSA of AD involvement at the Baseline Visit. 4. Baseline weekly average of daily WP-NRS ≥ 4. 5. Documented history of inadequate response to previous systemic treatment defined as documented history of previous inadequate response to at least one prior systemic treatment for AD OR for whom other systemic treatments are otherwise medically inadvisable.
Study Drug and Duration of Treatment:	
In Period 1, subjects who meet eligibility criteria will be randomized in a 1:1 ratio to receive either upadacitinib 15 mg QD or dupilumab as per its label. At Week 16 subjects from both treatment arms with a < EASI 75 response will enter Period 2; subjects from the dupilumab arm will be offered the option to receive upadacitinib 15 mg QD while subjects from the upadacitinib arm will either continue (if already receiving 30 mg QD) or be escalated to upadacitinib 30 mg QD (if receiving 15 mg QD) until Week 32.

Date of Protocol Synopsis:	02 May 2023

2 INTRODUCTION

2.1 Background and Rationale

Why Is This Study Being Conducted?

The Janus kinase (JAK) or JAKs are a family of intracellular tyrosine kinases that function as dimers in the signaling process of many cytokine receptors.¹ The JAKs play a critical role in both innate and adaptive immunity, making them attractive targets for the treatment of inflammatory diseases.²⁻⁵ Targeting the JAK signaling pathway for autoimmune diseases is supported by the involvement of various proinflammatory cytokines that signal via JAK pathways in the pathogenesis of these immune-related disorders. The activation of JAK signaling initiates expression of survival factors, cytokines, chemokines, and other molecules that facilitate leukocyte cellular trafficking and cell proliferation, which contribute to inflammatory and autoimmune disorders.

Upadacitinib is an oral, once-daily, selective, and reversible small-molecule JAK inhibitor, engineered to have greater inhibitory potency for JAK1 versus JAK2, JAK3, and tyrosine kinase 2 (TYK2). Janus kinase 1 inhibition blocks the signaling of many important pro-inflammatory cytokines, including interleukin (IL)-2, IL-6, IL-7, and IL-15, interferon (IFN)- γ , which are known contributors to inflammatory disorders. It also blocks the signaling of IL-4, IL-13, IL-31, IL-22, IFN γ , and thymic stromal lymphopoietin (TSLP) cytokines that play an important role in the pathogenesis of atopic dermatitis (AD). To date, upadacitinib has been approved in at least one country for rheumatoid arthritis (RA), psoriatic arthritis (PsA), ankylosing spondylitis (AS), non-radiographic axial spondyloarthritis (nr-axSpA), ulcerative colitis (UC), Crohn's disease (CD), and atopic dermatitis (AD). Upadacitinib is also being investigated for patients with giant cell arteritis (GCA), Takayasu arteritis, polyarticular course juvenile idiopathic arthritis (pcJIA), systemic juvenile idiopathic arthritis (sJIA), pediatric AD, pediatric UC, nonsegmental vitiligo, hidradenitis suppurativa (HS), alopecia areata and systemic lupus erythematosus (SLE).

Additional information regarding indications under study can be found in the current edition of the upadacitinib Investigator's Brochure.

In AD, the efficacy and safety of upadacitinib 15 mg and 30 mg once daily (QD) was assessed in three Phase 3 randomized, double-blind, multicenter studies (MEASURE UP 1, MEASURE UP 2 and AD UP),⁶⁻⁸ and the two doses (upadacitinib 15 mg and 30 mg QD) studied in the pivotal trials for AD were approved for the treatment of moderate to severe AD in several jurisdictions, including but not limited to the European Union (EU), Japan, Canada, and the United States (US), with some differences in the indications or posologies.⁹ However, the Phase 3 studies for AD were designed with a stable regimen of upadacitinib 15 mg or 30 mg QD for 5 years and no dose escalation or dose reduction based on the clinical response were assessed.

In addition, the efficacy and safety of upadacitinib 30 mg QD versus dupilumab for the treatment of adult subjects with moderate to severe AD who were candidates for systemic therapy was assessed in a head-to-head, Phase 3b, multicenter, randomized, double-blinded, double-dummy, active-controlled clinical trial (HEADS UP).^{10,11} However, the 15 mg QD dose for upadacitinib was not assessed in that trial.

Dupilumab is a recombinant human IgG4 monoclonal antibody that inhibits interleukin-4 and interleukin-13 signaling. Dupilumab inhibits IL-4 signaling via the Type I receptor (IL-4R α / γ c), and both IL-4 and IL-13 signaling through the Type II receptor (IL-4R α /IL-13R α).

Dupilumab has been approved in at least one country for the treatment of moderate to severe AD, moderate to severe asthma, chronic rhinosinusitis with nasal polyposis, eosinophilic esophagitis, and prurigo nodularis.

In AD, dupilumab has been approved for the treatment of moderate-to-severe AD in adults and adolescents 12 years and older who are candidates for systemic therapy, and for the treatment of severe AD in children 6 to 11 years old who are candidates for systemic therapy in the EU and for the treatment of adult and pediatric patients aged 6 months and older with moderate-to-severe AD whose disease is not adequately controlled with topical prescription therapies or when those therapies are not advisable in the United States (US).¹²

The efficacy and safety of dupilumab as monotherapy and with concomitant topical corticosteroids (TCS) were evaluated in three pivotal randomized, double-blind, placebo-controlled, multicenter studies (SOLO 1, SOLO 2, and CHRONOS)^{13,14} in 2,119 patients 18 years of age and older with moderate to severe AD. The efficacy and safety of dupilumab monotherapy in adolescent patients was evaluated in a randomized, double-blind, placebo-controlled, multicenter study (AD-1526)¹⁵ in 251 adolescent patients 12 to 17 years of age with moderate-to-severe AD.

This study aims to provide data on the efficacy and safety of upadacitinib initiated at 15 mg QD and dose escalated based on the clinical response, compared with dupilumab as per its label, after 16 weeks of treatment.

Additionally, this study aims to provide data on the efficacy and safety of upadacitinib initiated at 15 mg QD and dose adjusted based on clinical response in subjects with inadequate response to dupilumab.

Clinical Hypothesis

The primary hypothesis is that upadacitinib, initiated at 15 mg QD and dose escalated based on clinical response will demonstrate superior efficacy compared to dupilumab and will be well tolerated in adult and adolescent subjects with moderate to severe AD who have inadequate response to a systemic therapy.

2.2 Benefits and Risks to Subjects

In the EU SmPC, upadacitinib has been approved for the treatment of moderate to severe AD in adults and adolescents 12 years and older who are candidates for systemic therapy.⁹

The recommended dose is upadacitinib 15 mg or 30 mg QD based on individual patient presentation. A dose of 15 mg QD is recommended for patients with risk factors for venous thromboembolism, major adverse cardiovascular events (MACE), and malignancy. A dose of 30 mg QD may be appropriate for patients with high disease burden who have no known risk factors for venous thromboembolism, MACE, and malignancy, or for patients with an inadequate response to 15 mg QD. The lowest effective dose for maintenance should be used.⁹

For patients ≥ 65 years of age the recommended dose is upadacitinib 15 mg QD.⁹ The recommended dose of upadacitinib for adolescents (from 12 to 17 years of age) weighing at least 30 kg is upadacitinib 15 mg QD.⁹ The above indication and posology correspond to the European Union and may vary within different jurisdictions.

In the US USPI, upadacitinib has been approved for adults and pediatric patients 12 years of age and older with refractory, moderate to severe AD whose disease is not adequately controlled with other systemic drug products, including biologics, or when the use of those therapies are inadvisable. Upadacitinib is not recommended for use in combination with other JAK inhibitors, biologic immunomodulators, or with other immunosuppressants.

The recommended dosage for pediatric patients 12 years of age and older weighing at least 40 kg and adults less than 65 years of age is to initiate treatment with 15 mg once daily. If an adequate response is not achieved, consider increasing the dosage to 30 mg once daily. Discontinue upadacitinib if an adequate response is not achieved with the 30 mg dose. Use the lowest effective dose needed to maintain response.

The efficacy and safety of upadacitinib 15 mg and 30 mg QD was assessed in 3 Phase 3 randomized, double-blind, multicenter studies (MEASURE UP 1, MEASURE UP 2, and AD UP) in a total of 2584 subjects (12 years of age and older).⁶⁻⁸ A significantly greater proportion of subjects treated with upadacitinib 15 mg or 30 mg QD achieved validated Investigator's Global Assessment for AD (vIGA-AD) 0 or 1, Eczema Area and Severity Index (EASI) 75, EASI 90, EASI 100, Dermatology Life Quality Index (DLQI) 0 or 1, or a ≥ 4 -point improvement on the Worst Pruritus Numerical Rating Scale (WP-NRS) compared to placebo at Week 16. Rapid improvements in skin clearance and itch were also achieved. Results at Week 16 were maintained through Week 52 in subjects treated with upadacitinib 15 mg or 30 mg QD.

Adverse events (AEs) such as infections including herpes zoster reactivation, major adverse cardiovascular events (MACE defined as cardiovascular death, non-fatal myocardial infarctions, and non-fatal strokes), thrombosis, malignancies, hypersensitivity (serious anaphylactic reaction and angioedema), gastrointestinal perforation, bone fracture, and some laboratory abnormalities have been observed in patients receiving JAK inhibitors including upadacitinib.

An increased risk of infections including opportunistic infections (e.g., mucosal candida infections) and herpes zoster, non-melanoma skin cancer (NMSC), and abnormal laboratory changes (e.g., elevations of serum transaminases, lipids, creatine phosphokinase [CPK], and reductions in hemoglobin and white blood cells [WBC]) have been observed with upadacitinib therapy.

In ORAL Surveillance, a study of a different JAK inhibitor, tofacitinib, in RA patients 50 years of age and older with at least one cardiovascular risk factor, higher rates of all-cause mortality, malignancies, MACE and thrombosis (overall thrombosis, deep vein thrombosis, and pulmonary embolism) were seen in patients treated with tofacitinib versus TNF blockers.^{7,16} These higher rates were primarily observed in patients 65 years of age and older, patients with a history of atherosclerotic cardiovascular disease, and current or past long-time smokers. Although upadacitinib clinical trial data to date have not indicated a higher risk for MACE, venous thromboembolism, malignancies excluding NMSC, or deaths in RA patients treated with upadacitinib versus adalimumab, the findings of the ORAL Surveillance study may also apply to other JAK inhibitors and an increased risk for these events compared to TNF blockers cannot be completely excluded. Therefore, the investigator should consider the benefits and risks of upadacitinib treatment and suitable treatment alternatives in determining study participation and the continued use

of upadacitinib in patients 65 years of age and older, patients with a history of atherosclerotic cardiovascular disease or other cardiovascular risk factors, patients who are current or past long-time smokers, and/or patients with other malignancy risk factors (e.g., current malignancy or history of malignancy).

The results of genetic toxicology testing indicate that upadacitinib is not genotoxic; however, upadacitinib is teratogenic based on animal studies, which necessitates avoidance of pregnancy in females of childbearing potential. Based on the calculated safety margins for human fetal exposure with seminal fluid transfer, there is judged to be no risk to the pregnancy of female partners of male subjects who are treated with upadacitinib.

A detailed discussion of the pre-clinical and clinical toxicology, metabolism, pharmacology, and safety experience with upadacitinib can be found in the current Investigator's Brochure.

Taken together, the safety and efficacy data from upadacitinib studies to date show a favorable benefit:risk profile for upadacitinib and support the continued investigation of upadacitinib in patients with various immune-mediated inflammatory conditions.

Dupilumab has been approved for the treatment of moderate-to-severe AD in adults and adolescents 12 years and older who are candidates for systemic therapy, and for the treatment of severe AD in children 6 to 11 years old who are candidates for systemic therapy in the EU¹⁷ and for the treatment of adult and pediatric patients aged 6 months and older with moderate-to-severe AD whose disease is not adequately controlled with topical prescription therapies or when those therapies are not advisable in the United States (US).¹²

Although dupilumab addresses the needs of some patients with moderate to severe AD, a large unmet need still exists in this population since, in the dupilumab Phase 3 studies (even when combined with topical corticosteroids [TCS]), fewer than 40% of the adult patients achieved 0 or 1 on the Investigator's Global Assessment (IGA) scale.^{13,14} This percentage was lower for adolescents, as 24.4 % of subjects included in the study achieved a 0 or 1 on the IGA at Week 16.

Therefore, a large proportion of patients continued to experience significant symptoms on dupilumab therapy. Nearly 50% of dupilumab adult subjects who were IGA 0 or 1 responders at Week 16 became nonresponders by Week 52.¹⁷ Dupilumab is generally well-tolerated, and the most common adverse events (AEs) are injection site reaction, conjunctivitis, and blepharitis.

Considering the coronavirus – 2019 (COVID-19) pandemic and based on the information to date, it is unknown whether study participants treated with upadacitinib may be at an increased risk for COVID-19 or experience more serious illness if infected. The data thus far do not show that patients on upadacitinib treatment have worse outcomes of COVID.

For further details, please see findings from completed studies, including safety data in the current upadacitinib Investigator's Brochure.^{18,19}

3 OBJECTIVES AND ENDPOINTS

3.1 Objectives, Hypotheses, and Estimands

Objectives

Primary

The primary study objective, related to Study Period 1, is to assess the efficacy and safety of upadacitinib, initiated at 15 mg once daily (QD) and dose adjusted based on clinical response, compared with dupilumab as per its label.

An additional objective, related to Study Period 2, is to assess the efficacy and safety of upadacitinib, initiated at 15 mg QD and dose adjusted based on clinical response, in subjects with inadequate response to dupilumab.

The primary efficacy objective is based on the achievement of a composite endpoint of at least a 90% reduction in EASI from baseline (EASI 90) and a Worst Pruritus Numerical Rating Scale of 0 or 1 (WP-NRS 0/1) at Week 16 with the treatment of upadacitinib compared with dupilumab per its label in the Intent-to-Treat (ITT) Population, which consists of all randomized subjects (Section 7.2).

Secondary

The secondary efficacy objectives are based on ranked secondary endpoints as defined in Section 3.3 with the treatment of upadacitinib compared with dupilumab in the ITT Population.

Hypotheses and Estimands for the Primary and Ranked Secondary Endpoints

The hypothesis corresponding to the primary efficacy endpoint (Section 3.2) is:

- The proportion of subjects achieving both EASI 90 and WP-NRS 0/1 at Week 16 in those treated with upadacitinib is greater than those treated with dupilumab.

The estimand corresponding to the primary endpoint is defined using the composite variable strategy, as follows:

- Difference in the proportion of subjects achieving both EASI 90 and WP-NRS 0/1 at Week 16 without the use of rescue medication, regardless of treatment discontinuation, between upadacitinib and dupilumab in the adolescent and adult subjects with moderate to severe AD who have inadequate response to systemic therapy.

The hypotheses and estimands corresponding to the ranked secondary endpoints are summarized below.

- Hypotheses: the proportion of subjects achieving each ranked endpoint in those treated with upadacitinib is greater than those treated with dupilumab

- Estimands: Difference in proportion of subjects achieving each of ranked secondary endpoints without the use of rescue medication, regardless of treatment discontinuation, between upadacitinib and dupilumab in the adolescent and adult subjects with moderate to severe AD who have inadequate response to systemic therapy.

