3.3 Secondary Endpoints

Ranked Secondary Endpoints

1. Achievement of EASI 90 at Week 16.
2. Achievement of WP-NRS 0/1 at Week 16 among subjects with Baseline WP-NRS > 1.
3. Achievement of an improvement (reduction) in WP-NRS ≥ 4 at Week 16 among subjects with Baseline WP-NRS ≥ 4 .
4. Achievement of WP-NRS 0/1 at Week 4 among subjects with Baseline WP-NRS > 1.
5. Achievement of WP-NRS 0/1 at Week 2 among subjects with Baseline WP-NRS > 1.
6. Achievement of EASI 90 at Week 4.
7. Achievement of EASI 75 at Week 2.
8. Achievement of EASI 100 at Week 16.

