7.8 Overall Type I Error Control

The statistical comparisons of upadacitinib versus dupilumab for the primary efficacy endpoint and the ranked secondary endpoints will be carried out in the hierarchical order under a 2-sided significance level of 0.05. This means that statistically significant results for the comparison in the higher rank (primary, then ranked secondary endpoints) are necessary to initiate the testing of the next comparison in the lower rank. Since a step-down procedure is used, each comparison will be tested at a significance level of 0.05 and the family-wised error rate is strongly controlled at 0.05.

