7.9 Sample Size Determination

Approximately 880 subjects will be randomized to upadacitinib or dupilumab in a 1:1 ratio. Assuming a response rate of 12% in achieving both EASI 90 and WP-NRS 0/1 at Week 16 in the dupilumab group, this sample size will provide more than 90% power to detect the treatment difference of 17% (upadacitinib versus dupilumab), using a two-sided significant level of 0.05.

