  IF 0<=WK16<=0.9*BASE THEN EASI90_16=1;
  ELSE EASI90_16=0;
RUN;

/*****
*/
/* DATA HANDLING STEPS TO MERGE COVID 19 or Other MAR STATUS OMITTED
*/
/* PLACE TO ADD DATA HANDLING AND MERGING STEPS
*/
/*****
*/

/*FOR MI, SKIP THE FOLLOWING CODE, PROCEED TO THE CODE AFTER ANALYSIS
MODEL *//*OVERRIDE MISSING VALUES NOT DUE TO COVID 19 or Other MAR WITH
TRADITIONAL NRI*/
DATA ALLF; SET ALL;
  /*COVID19_XX='Y' IF MISSING AT WEEK XX IS DUE TO COVID 19 or Other
MAR; IF NOT, OVERRIDE WITH TRADITIONAL NRI*/

```

```

    IF COVID19_2 NE 'Y' THEN EASI90_2=EASI90NRI_2;
    IF COVID19_4 NE 'Y' THEN EASI90_4=EASI90NRI_4;
    IF COVID19_8 NE 'Y' THEN EASI90_8=EASI90NRI_8;
    /*VARIABLE EASI90NRI XX: TRADITIONAL NRI DATA AT WEEK XX, WHICH COVERS
    THE SPECIAL HANDLING SUCH AS THE BEFORE AND AFTER EXCEPTION*/
    IF COVID19_12 NE 'Y' THEN EASI90_12=EASI90NRI_12;
    IF COVID19_16 NE 'Y' THEN EASI90_16=EASI90NRI_16;
  RUN;
  PROC SORT DATA=ALLF; BY _IMPUTATION_ SUBJID; RUN;

  /*****/
  /*ANALYSIS MODEL*/
  /*****/

  /*KEY CODE: ANALYZING EACH 'COMPLETE' DATASET*/
  /*****/
  /*COMPARE TREATMENT GROUPS 1 (Dupilumab) AND 2 (Upadacitinib) ONLY*/
  DATA ALL; SET ALL;
    WHERE TRT01PN IN (1,2);
  RUN;

  /*INDIVIDUAL LEVEL DATA > # OF RESPONDERS & # OF SUBJECTS, TO BE READ
  IN TO PROC STDRATE*/
  PROC FREQ DATA=ALL;
    BY IMPUTATION ;
    TABLES TRT01PN*AGEGR1N*VIGAGR1N*EASI90_16/LIST NOCUM NOPRINT
  OUT=COUNT_TABLE;
    /*WEEK 16 RESULTS AS AN EXAMPLE*/
  RUN;
  DATA COUNT_TABLE; SET COUNT_TABLE;
    DROP PERCENT;
  RUN;
  PROC TRANSPOSE DATA=COUNT_TABLE OUT=FREQ_TABLE PREFIX=RESP;
  ID EASI90_16;
  BY IMPUTATION_ TRT01PN AGEGR1N VIGAGR1N;
  VAR COUNT;
  RUN;
  DATA FREQ_TABLE1; SET FREQ_TABLE;
    CASE=RESP1;
    SIZE=SUM(RESP0, RESP1);
    KEEP _IMPUTATION_ TRT01PN AGEGR1N VIGAGR1N CASE SIZE;
  RUN;

  /*RE ORDER TO SET 1 (Dupilumab) AS THE REFERENCE GROUP*/
  DATA FREQ_TABLE2; SET FREQ_TABLE1;
    IF TRT01PN=2 THEN TRT01PN=0;
  RUN;

  /*CALCULATE THE COMMON RISK DIFF FOR EACH COMPLETE DATASET*/

```

```
PROC STDRATE DATA=FREQ TABLE2  
  METHOD=MH STAT=RISK EFFECT=DIFF;  
  BY _IMPUTATION_;  
  POPULATION GROUP=TRT01PN EVENT=CASE TOTAL=SIZE;  
  STRATA AGEGR1N VIGAGR1N / ORDER=DATA STATS (CL=NONE) EFFECT;  
  ODS OUTPUT EFFECT=EFFECT;  
RUN;
```

```
/*COMBINING RESULTS USING PROC MIANALYZE*/  
/*****  
PROC MIANALYZE DATA=EFFECT;  
  ODS OUTPUT PARAMETERESTIMATES=RISK_DIFF_MH;  
  MODELEFFECTS RISKDIFF;  
  STDERR STDERR;  
RUN;
```

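### The SAP's sample code passes a zero responder count on as missing, which may drop whole strata from the Mantel-Haenszel difference when an endpoint is rare

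*Protocol*

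**What the plan says.** Protocol 3.1 defines the estimand for each ranked endpoint as the "Difference in proportion of subjects achieving each of ranked secondary endpoints without the use of rescue medication" between the two arms. SAP 9.4.2 analyses these endpoints by CMH on ITT 1, stratified by vIGA-AD (two levels) and age (three levels), which makes six strata. Appendix H 2.5.1 and 2.5.2 estimate the difference and its standard error in each of 30 imputed datasets, combine them by Rubin's rules, and base tests and confidence intervals on the result.

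Appendix H 3.0 gives sample code for this:

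- The counting step is "TABLES TRT01PN*AGEGR1N*VIGAGR1N*EASI90_16/LIST NOCUM NOPRINT", written to an output dataset without the SPARSE option.
- The counts are transposed to `RESP0` and `RESP1`.
- The denominator is "SIZE=SUM(RESP0, RESP1)", while the responder count is the plain assignment `CASE=RESP1`.
- PROC STDRATE then reads `CASE` as the event count and `SIZE` as the total.

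The only sparse-stratum rule is in SAP 9.6. It covers subgroup analyses and strata with no subjects in an arm, not strata with subjects but no responders.

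The ranked list includes early or strict endpoints, such as rank 5: "Achievement of WP-NRS 0/1 at Week 2 among subjects with Baseline WP-NRS > 1". Under Protocol 7.8, significant results at a higher rank "are necessary to initiate the testing of the next comparison in the lower rank".

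**The concern.** Without SPARSE, a combination that does not occur gets no row in the output. If an arm has no responder in a stratum, `RESP1` is missing after the transpose and so is `CASE`. `SUM()` ignores missing values, so the denominator survives. The numerator has no such protection, and no later step resets it to 0.

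An observed zero is data. If the row is discarded, the stratum has only one arm left and contributes nothing to the difference, so subjects in both arms are lost because of their outcome. The estimate would then no longer cover the ITT 1 population that the text specifies. Under multiple imputation, the same stratum could be present in some datasets and absent in others, and Rubin's rules would combine estimates over different sets of strata. A lost rejection at one rank would also close every rank below it.

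**Working it through.** **Inputs from the documents.** "Approximately 880 subjects will be randomized to upadacitinib or dupilumab in a 1:1 ratio" gives 440 per arm. The only planning rate is "Assuming a response rate of 12% in achieving both EASI 90 and WP-NRS 0/1 at Week 16 in the dupilumab group", with a difference of 17 points, hence 12% v 29%. There are six strata and a two-sided alpha of 0.05.

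**Assumed, because the documents do not say.** Subjects per arm in each stratum, in the order adolescents, 18 to <40, 40 to <64, with vIGA-AD 3 then 4 in each:

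- Layout A (10% adolescents, 40% vIGA-AD 4): 26, 18, 143, 95, 95, 63.
- Layout B (20% and 45%): 48, 40, 117, 95, 77, 63.
- Layout C: age shares 13/50/37%, 45% vIGA-AD 4.

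All rates other than 12% v 29% are illustrative. A stratum with a missing count is taken to contribute nothing.

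**1. The plan's own figure.** The SE under the null is √(2 × 0.205 × 0.795/440) = 0.0272. Under the alternative it is √((0.12 × 0.88 + 0.29 × 0.71)/440) = 0.0266. Power = Φ((0.17 − 1.96 × 0.0272)/0.0266) = Φ(4.38), above 99.9%. This agrees with "more than 90% power to detect the treatment difference of 17" points.

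**2. Chance of an empty responder cell.** With n subjects at rate p it is (1 − p)^n. For the primary in layout A, the two adolescent dupilumab cells give 0.88^18 = 10.0% and 0.88^26 = 3.6%. At least one is empty with probability 1 − 0.900 × 0.964 = 13%. For 26 subjects at lower rates: 0.97^26 = 45% and 0.98^26 = 59%.

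**3. Effect on power.** The estimator is RD = Σ w(x₁/n₁ − x₀/n₀)/Σ w with w = n₁n₀/(n₁ + n₀), and the Greenland-Robins SE. It was simulated without missing data, once with zeros entered as 0 and once with a stratum removed if either arm had no responder. Rates are equal across severity.

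| Dupilumab v upadacitinib | Layout | Chance a stratum drops | Power, zeros kept | Power, strata dropped |
|---|---|---|---|---|
| 12% v 29% | A / B | 13% / 1% | >99.9% | >99.9% |
| 5% v 12% | B | 26% | 96.9% | 95.7% |
| 5% v 10% | A / B | 67% / 28% | 82% | 78% / 78% |
| 3% v 10% | A / B | 86% / 62% | 99% | 98% / 97% |
| 3% v 8% | A / B | 88% / 64% | 92% | 85% / 83% |
| 2% v 7% | C | 93% | 96% | 84% |
| 2% v 6% | A / B | 97% / 87% | 88% | 70% / 65% |
| 1% v 5% | A / B | >99% / 99% | 96% | 59% / 49% |
| 1% v 10% | A / B | >99% / 99% | >99.9% | 95% / 94% |

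Layout C gives 54% at 1% v 5%. There, about 360 (A) to 410 (B) of the 880 subjects are lost on average, and the mean difference falls from 4.0 to 3.3 to 3.5 points.

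If vIGA-AD 4 rates are half those of vIGA-AD 3 (layout A), the chance of a drop for the primary rises to 28%, still with no power loss. Power at 5% v 10% is 77%. At 1% v 5% it is 66%, and the mean difference stays near 4.0 points.

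**4. Type I error.** With equal rates in layout A and strata dropped, upper-tail rejection is 2.1% at 5%, 1.4% at 3% and about 0% at 1%, against a nominal 2.5%.

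**5. Which empty strata cost power.** Take layout A with 29 more responders on upadacitinib overall. With equal arms, RD = 29/440 = 6.59 points, SE 1.47, z = 4.50. Suppose the 18-per-arm stratum has no responders in either arm. Dropping it gives 29/422 = 6.87 points, but the SE also rises by 440/422, so z stays at 4.50. Now drop as well a 26-per-arm stratum whose only 3 responders are on upadacitinib: 26/396 = 6.57 points, SE 1.58, z = 4.17. Power falls only through strata with responders in one arm and none in the other.

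The multiple-imputation effect was not sized, because the simulation contains no imputation.

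**The case against.** The listing is headed as sample code, uses Week 16 EASI 90 as its example, and says that data-handling steps are left out. The SAP text plans CMH on ITT 1 and excludes no stratum. Nothing in the documents says how PROC STDRATE treats a missing event count. As printed, the example calls a subject an EASI 90 responder at `<=0.9*BASE`, which needs only a 10% reduction, so empty responder cells would be rare.

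The power loss also rests on unsourced rates. Ranks 1 and 2 are components of the primary composite, so under the plan's own assumption their dupilumab rates are at least about 12%. Even a rare endpoint loses little if the difference is large (3% v 10%: 99% to 97 or 98%).

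All of this stands, and it limits the point to a conditional one. It does not remove the defect. This listing is the SAP's only detailed specification of the estimator, a missing count is not the intended 0 whatever the procedure does with it, and no text repairs it. The threshold line hides the problem only until that line is corrected.

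A reader might infer more: that the low-rate ranked endpoints will lose power, that rank 5 will fail and block ranks 6 to 8, that the primary is at risk, or that false positives rise. The documents give no rates or stratum sizes to support the first two, and the calculations contradict the last two. Nor is the estimand in Protocol 3.1 at fault; the defect lies in Appendix H 3.0.

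**Conclusion.** The code in SAP Appendix H 3.0 is wrong as written: it carries a missing value where an observed zero belongs, contrary to the planned CMH analysis on ITT 1. The consequence is conditional on three things: PROC STDRATE excluding rows with a missing event count, the sample code being reused for the ranked endpoints, and the unknown rates and stratum sizes.

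Under the assumed layouts, power for the primary is unaffected, with about a 1 to 13% chance that a stratum drops when rates are equal across severity. For ranked endpoints the loss is about 1 to 4 points at a 5% dupilumab rate. It becomes large only when that rate is about 1 to 3% and the absolute difference is small: 96% to about 84% at 2% v 7%, and 96% to about 49 to 59% at 1% v 5%. Type I error is not inflated. Strata with no responders in either arm change the estimate but not the power. Any failure that did result would stop testing at all lower ranks.

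**What to change.** In Appendix H 3.0, write `CASE=SUM(RESP1,0)`, or add SPARSE to the PROC FREQ TABLES statement. State in Appendix H 2.5.1 that a stratum with subjects but no responders enters with a count of 0.

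Add a check in each imputed dataset that the PROC STDRATE sizes in each arm sum to that endpoint's eligible ITT 1 denominator. This is all of ITT 1 for the primary and the EASI endpoints, and the set restricted by baseline WP-NRS for ranks 2 to 5. A check against the full ITT 1 total would be wrong for those four ranks.

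Correct the EASI 90 threshold line at the same time; otherwise a test run on the example may never meet an empty responder cell.

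The cost is one line of code and one check. Results are unchanged when no empty responder cell occurs.
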